### 13.2.3.5. Safety Data Analysis

Adverse Events and Serious Adverse Events – AEs will be categorized using Medical Dictionary for Regulatory Activities (MedDRA) Version 10.0 or later. The intensity of toxicities will be graded by the Investigator as mild, moderate, or severe as described in Section 12.2.5. Serious Adverse Events (SAEs) will be a subset of the overall AE analysis and may be analyzed in a similar manner.

The calculation of AE incidence will be based on the number of patients per AE category. For each patient who has multiple AEs classified to the same category, that patient will be tabulated under the maximum toxicity intensity for that AE category. The incidence of AEs will be tabulated by MedDRA system organ class and preferred term, as well as by treatment group.

An AE onset between the date of the first dose of study drug and 30 days after the last dose of study drug is considered as a treatment-emergent AE.

- Laboratory Safety Data – Hematology, chemistry, and urinalysis data will be summarized by timepoint of collection and by treatment group. In addition, out-of-normal range values will be listed.
- Other Safety Data – the results of antibodies against EZN-2279, antibodies against Adagen®, and antibodies against PEG will be summarized. The relationships between immunogenicity, PK, and the clinical toxicities will be examined as appropriate.

Concomitant medications and findings in physical examinations will be described textually as recorded in the CRF.

Descriptive statistics of vital signs measurements as well as changes from baseline will be tabulated.

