7.2 Study Drug Administration

Study drug administration for both Adagen[®] and EZN-2279 will be summarized. Duration of treatment (days treated) is the number of days on each treatment based on the first and last days of treatment with each study drug (last day of study drug – first day of study drug + 1). The number and percent of patients and the number of doses within categories for weeks on treatment will be summarized for Adagen[®]. The percent of patients and the number of doses within categories for months of treatment for EZN-2279 during the EZN-2279 treatment period, and months of treatment combining the EZN-2279 treatment and maintenance periods will be summarized with categories. Duration of treatment (days) will also be summarized as a continuous variable for Adagen[®], EZN-2279 treatment, and overall EZN-2279 (treatment plus maintenance) using descriptive statistics.

Administration of both Adagen[®] and EZN-2279 will be listed.

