7.3 Adverse Events and Other Complications

All adverse events will be coded using the Medical Dictionary for Regulatory Activities (MedDRA) Version 16.0 or the most recent version prior to database lock. Summaries will be presented for all treatment-emergent adverse events (overall and by severity), adverse events determined by the investigator to be treatment-related (overall and by severity), serious adverse events (SAEs), adverse events causing discontinuation from study, adverse events causing discontinuation from study drug, and non-serious adverse events. In addition to being summarized as adverse events, infectious complications and hospitalizations are considered efficacy measures as are summarized in Section 6.3.

The frequency of adverse events will be summarized using descriptive statistics by system organ class (SOC), preferred term and study drug group. Patients are counted only once in each SOC category, and only once in each preferred term category.

Treatment-related adverse event summaries will include adverse events with missing relationship to study drug. For the summaries by severity, patients are counted at the greatest severity. Adverse events missing the flag indicating serious will be excluded from the summary of serious adverse events but included in the summary of non-serious adverse events.

There will be two treatment emergent adverse event summaries provided: all treatment emergent adverse events while the patient takes Adagen[®] study drug and all treatment emergent adverse events while the patient takes EZN-2279, where treatment emergent are new or worsening adverse events that occur while on the respective therapies.

Listings for all adverse events, deaths, serious adverse events, adverse events leading to discontinuation, MedDRA dictionary terms for adverse event descriptions, and adverse event preferred terms by patient number will be presented.

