10.6 Safety Data Handling

For the purposes of AE reporting, three time periods will be defined based upon the onset date of the AE:

- “Pre-treatment AEs” are AEs with onset dates < date of the first dose of Adagen[®] study medication.
- “Treatment-emergent AEs” are AEs with onset dates \geq date of the first dose of study medication and within 30 days following the date of the last dose of study medication.
- “Post-treatment AEs” are AEs with onset dates > 30 days after the date of the last dose of study medication, within study STP-2279-002.

“Pre-treatment” and “Post-treatment” AEs are considered non-treatment-emergent AEs. For AEs with partially missing onset dates, an onset date is imputed as detailed in Section 12 (Programming Specifications). If an AE has a completely missing onset date, it is

counted as a “treatment-emergent” event, unless the stop date is on or before the date of the first dose of study medication.

If relationship to study drug is missing, for analysis purposes it will be assumed to be related to study drug. For AEs which occur more than once within a time period (see above), the AE which is most related to study drug in that time period will be used in the summary of AEs by categories of relationship to study drug. Similarly, the AE with the maximum intensity in that time period will be used in the summary of AEs by categories of severity.

For each study drug (EZN-2279 or Adagen[®]) medications will be assigned to a time period as follows:

- Medications taken any time < date of the first dose of Adagen[®] during the Lead-in phase will be considered prior medications.
- Medications can be concomitant with either Adagen[®], EZN-2279, or both. Medications taken any time \geq date of the first dose of respective study medication and within 30 days following the date of the last dose of respective study medication will be considered concomitant medications for that study drug.
- Medications taken > 30 days after the date of the last dose of respective study medication will be considered “post treatment” medications for that study drug.

Note that medications can be counted in more than one category (i.e., prior/concomitant) and can have different assignments for different study drugs. Imputation rules for partially missing start/stop dates are described in Section 12 (Programming Specifications).

Change from baseline to Week X in safety endpoints will be calculated as:

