- The following specifications apply to tables that summarize categorical data unless otherwise noted:
 - Percent of events should be left blank (including the parentheses) if the number of events is zero.
 - If the categories of a parameter are ordered, then all categories between the maximum possible category and the minimum category should be included, even if n=0 for a given category between the minimum and maximum level for that parameter.

- If the categories are not ordered, then only those categories for which there is at least one Patient represented should be included.
- A ‘Missing’ category should be added to any parameter for which information is not available for any patients.
- Missing data should be represented on listings as 1) dashes “-”, and properly footnoted: “ - = data not available” or 2) “N/A”, with footnote “N/A” = Not Applicable”, whichever is appropriate.
- Times should be printed in the format “HH:MM”. “HH” represents the 2-digit hour portion of the time. “MM” represents the 2-digit minute portion of the time. Both hour and minute portions of time are zero-filled on the left if they have only one digit. Missing time portions should be represented on patient listings as dashes (“10:--” and “--:--”). Times that are missing because they are not applicable for the patient should be printed as “N/A” unless otherwise specified.
- Adverse event summary tables will only include treatment-emergent AEs. However, listings will include all AEs (i.e., treatment-emergent and non treatment-emergent AEs) with the non treatment-emergent AEs flagged.

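### SAP 7.3 gives the by-drug adverse event tables no post-dose tail, while SAP 10.6 and the protocol run to 30 days after the last dose and do not say which drug's table takes those days

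*SAP*

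**What the plan says.** SAP 7.3 commits to a pair of by-drug tables: "There will be two treatment emergent adverse event summaries provided: all treatment emergent adverse events while the patient takes Adagen", with a matching summary for EZN-2279. It then defines the term for those tables: "where treatment emergent are new or worsening adverse events that occur while on the respective therapies". No days after the last dose are mentioned.

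SAP 10.6 defines the same term differently. An AE is treatment-emergent if its onset is on or after the "date of the first dose of study medication and within 30 days following the date of the last dose of study medication". It becomes post-treatment only when onset is more than "30 days after the date of the last dose of study medication, within study STP-2279-002". These bullets speak of study medication in general and name neither drug.

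Protocol 13.2.3.5 agrees with SAP 10.6: "An AE onset between the date of the first dose of study drug and 30 days after the last dose of study drug" counts as treatment-emergent. Protocol 12.1 collects AEs to 30 days after the final EZN-2279 dose or, for patients withdrawn before the switch, 30 days after the final Adagen dose.

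The definition decides what is tabulated, because SAP section 11 states: "Adverse event summary tables will only include treatment-emergent AEs". Other events go to flagged listings. SAP 7.1, where departures from the protocol's safety analysis are declared, mentions only the data looks.

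**The concern.** Two sections of one SAP define the same term over different windows, and the narrower one sits in the section that specifies the by-drug tables. A programmer working from SAP 7.3 and another working from SAP 10.6 could produce different AE tables from the same data.

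The events at risk are those that begin after a patient has stopped all study drug, during the 30 days in which the protocol still collects AEs and still calls them treatment-emergent. Protocol 11.5.1 requires a safety visit with AE assessment at least 30 days after the last dose for early discontinuers, so these data will exist. The by-drug tables are a central safety display for a product that, per protocol 5.3.2, had no earlier clinical studies, and the trial seeks six evaluable patients. A single event shows in the percentages.

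**Working it through.** The plan gives no figure to reproduce. The check is a comparison of definitions followed by day counts.

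**1. Which days each rule covers for a patient who stops all study drug**

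| Source | End of window | Tail assigned to a drug? |
|---|---|---|
| SAP 7.3 | While on the drug concerned | No tail stated |
| SAP 10.6, AE bullets | Last dose + 30 days | No |
| Protocol 13.2.3.5 | Last dose + 30 days | No |
| Protocol 12.1 (collection) | Final EZN-2279 dose + 30 days, or final Adagen dose + 30 days if never switched | Yes |
| SAP 10.6, concomitant medications | Last dose of the respective drug + 30 days | Yes |

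Take an event with onset 10 days after the last injection and no further study drug. It is treatment-emergent under SAP 10.6 and the protocol. Under SAP 7.3 it belongs to neither drug's table.

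SAP 10.4 assigns AEs starting on the first EZN-2279 dose day to EZN-2279. It says nothing about time after stopping.

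**2. Length of the gap**

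SAP 7.3 does not define being on therapy. Two readings bound it:

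- It ends on the last dose day. The gap is 30 days.
- It includes the final weekly dosing interval (last dose day plus 6). The gap is 30 − 6 = 24 days. This is an assumption.

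**3. Gap as a share of the SAP 10.6 window**

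Share = gap / (day of last dose + 30), with days counted from the first dose of the drug concerned.

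| Last dose | Window (days) | 30-day gap | 24-day gap |
|---|---|---|---|
| Adagen lead-in Day 15 (three weekly doses, illustrative) | 15 + 30 = 45 | 30/45 = 66.7% | 24/45 = 53.3% |
| EZN-2279 Day 22 (T-4, illustrative early stop) | 22 + 30 = 52 | 30/52 = 57.7% | 24/52 = 46.2% |
| EZN-2279 Day 141 (T-21) | 141 + 30 = 171 | 30/171 = 17.5% | 24/171 = 14.0% |
| About 2 years of treatment | 730 + 30 = 760 | 30/760 = 3.9% | 24/760 = 3.2% |
| About 3 years of treatment | 1095 + 30 = 1125 | 30/1125 = 2.7% | 24/1125 = 2.1% |

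The 2- and 3-year rows use the treatment durations in protocol 7.4.1. All of these are shares of calendar time, not of events.

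**4. Weight of one patient**

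With six treated patients, 1/6 = 16.7 percentage points. A patient who stops before completing T-21 is unevaluable and is replaced (protocol 9.5.3). If six evaluable patients are then reached, at least seven have been treated: 1/7 = 14.3 points. SAP 7.3 counts a patient once per preferred term, so the incidence moves only if that term had not already occurred on the drug.

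**The case against.** The best defence is that SAP 10.6 governs. It sits under Rules and Definitions, sets out the AE time periods for reporting, supplies the split that section 11 applies to tables, and agrees with the protocol. On that view the SAP 7.3 sentence only divides treatment-emergent events between two drugs, and an event after stopping goes to the last drug received. This is a reasonable reading, and because of it the consequence has to be stated conditionally. It does not remove the problem. Nothing ranks SAP 10.6 above SAP 7.3, and the AE bullets never assign the tail to a drug, although the concomitant-medication rule in the same section does so.

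Three stronger claims might be inferred, and the documents do not support them.

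- **That time on therapy ends on the day of the last injection.** SAP 7.2 says "Duration of treatment (days treated) is the number of days on each treatment based on the first and last days of treatment", but that is for the exposure summary and nothing ties it to AE assignment. Applied to AEs, it would also leave the roughly 168 hours between a switching patient's last Adagen dose and first EZN-2279 dose in neither table. That fits poorly with the changeover rule in SAP 10.4. Hence the range of 24 to 30 days.
- **That the patients affected stop mainly for toxicity or antibodies, so the tables are seriously biased.** Protocol 9.5.1 lists many reasons for stopping and gives no frequencies. An event that causes stopping will ordinarily have begun on drug and is tabulated under either rule.
- **That the events are lost.** SAP 7.3 and section 11 put all AEs in listings, with separate listings of deaths, SAEs and AEs leading to discontinuation.

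**Conclusion.** The conflict between SAP 7.3 and SAP 10.6 with protocol 13.2.3.5 is in current text and is not declared as a change. If the by-drug tables are programmed literally from SAP 7.3, new-onset events in roughly the last 24 to 30 days of the protocol's window are omitted from both tables for any patient who stops all study drug. Compared with the 30-day rule, this can only lower tabulated incidence.

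The size depends on when patients stop. The calendar share is modest for a last dose at T-21 and small after years of maintenance, but it exceeds half for a stop after three lead-in doses. The effect is nil unless someone stops and then has a new or worsening event. Patients who switch on schedule are essentially unaffected, because their later events go to EZN-2279.

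The primary endpoint is untouched and the safety analysis is descriptive. The point still deserves correction before tables are programmed, because one patient is worth 14 to 17 percentage points in a trial of this size.

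**What to change.** In SAP 7.3, replace the clause quoted there with explicit windows:

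- **EZN-2279 table:** onset or worsening from the first EZN-2279 dose through 30 days after the last EZN-2279 dose.
- **Adagen table:** onset or worsening from the first lead-in dose up to the first EZN-2279 dose or, for patients never switched, through 30 days after the last lead-in dose, as in protocol 12.1.

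Reword the AE bullets in SAP 10.6 per drug to match. Closing the Adagen window at the switch keeps early EZN-2279 events from being counted twice and agrees with SAP 10.4. Copying the concomitant-medication rule unchanged would create that overlap.

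The cost is SAP wording and one programming rule. EZN-2279 AE counts may come out slightly higher and may include events after a patient has returned to other therapy, which a footnote can identify.

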7.4 Clinical Laboratory Tests

Summary statistics for chemistry, hematology, and urinalysis laboratory tests will be presented at baseline, each intermediate collection time-point, and endpoint. Laboratory tests results and changes from screening (for Adagen[®] drug group) or from the end of the Adagen[®] Lead-in period (for EZN-2279 drug group) to each visit and endpoint will be summarized using descriptive statistics.

Listings for laboratory data will be presented identifying clinically significant abnormal results. Results of pregnancy tests will be listed, but not summarized.

7.5 Vital Signs

Summary statistics for vital signs will be presented at baseline. Abnormal vital sign values will be reported and summarized as adverse events.

Actual vital sign values will be listed, but not summarized.

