#### 5.3.2. Clinical Studies

No clinical studies of EZN-2279 have been performed.

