## 7.6. Appropriateness of Study Measurements

In this study, for patients  $\geq 10$  years of age, pharmacokinetics will be assessed by repeated sampling for ADA activity following a dose and pharmacodynamics will be assessed by monitoring dAXP levels. These are assessments that are commonly used to monitor patients treated with Adagen®.

Safety in this study will be assessed by monitoring adverse events, laboratory parameters (serum chemistry, hematology, and urinalysis), physical examination changes and vital signs. These are standard assessments for monitoring safety in clinical trials. In addition, monitoring of binding and neutralizing antibodies is commonly used to monitor patients treated with Adagen®.

In addition to pharmacodynamics, efficacy will be assessed by monitoring trough ADA activity, immune status (ALC, lymphocyte subset analysis, quantitative immunoglobulins) and clinical evaluations (growth, incidence of infections and hospitalizations). These are assessments that are commonly used to monitor patients treated with Adagen®.

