#### 10.4.2. Vital Signs

Vital signs will include sitting systolic and diastolic blood pressure, pulse rate, respirations, and temperature. Blood pressure will be measured and recorded to the nearest millimeter of mercury (mmHg).

Clinically meaningful changes in vital signs made after the start of study drug, which meet the definition of an AE, must be recorded on the Adverse Event CRF.

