7.1 Changes to the Planned Safety Analysis Proposed in Protocol

The protocol called for interim analyses when three patients will be enrolled and complete through full EZN-2279 pharmacokinetic sampling (Week T-9) and again when six patients complete through 9-weeks of EZN-2279 dosing. There will be a third look that will be used for a BLA. In addition, there will be a final analysis (fourth analysis) on subjects who complete one year (two maintenance cycles).

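### SAP 7.5 omits, without declaring it, the protocol's table of vital signs and changes from baseline, so shifts too small to be reported as adverse events appear only in listings

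*SAP*

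**What the plan says.** Protocol 13.2.3.5 (Safety Data Analysis) commits to a table: "Descriptive statistics of vital signs measurements as well as changes from baseline will be tabulated". Protocol 7.6 counts vital signs among the safety assessments, naming "physical examination changes and vital signs" after adverse events and laboratory parameters. Protocol 10.4.2 adds a rule for what goes on the adverse event form: "Clinically meaningful changes in vital signs made after the start of study drug, which meet the definition of an AE, must be recorded".

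SAP 7.5 (Vital Signs) has three sentences. The first keeps one summary: "Summary statistics for vital signs will be presented at baseline". The second gives the adverse event route: "Abnormal vital sign values will be reported and summarized as adverse events". The third covers the remaining values: "Actual vital sign values will be listed, but not summarized". The section says nothing about change from baseline.

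SAP 7.1 is reserved for changes to the safety analysis planned in the protocol. It describes only the interim, BLA and final looks. Protocol 13.2.5 leaves it to the SAP to say how deviations from the statistical methodology are documented.

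**The concern.** The protocol promises a descriptive table and the SAP states the opposite rule, with no declaration or reason. This is a contradiction between two explicit statements, so it cannot be put down to detail left open.

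The protocol says of this product: "No clinical studies of EZN-2279 have been performed". Each patient serves as his or her own control, so within-patient change after the switch from Adagen is the natural comparison for a measured safety variable. If most patients showed a modest change in blood pressure, pulse, respiration or temperature, and no reading was judged an adverse event, no planned summary would show it. The route that remains depends on judgement, and protocol 7.5 itself says that adverse event assessment is open to bias because staff cannot be blinded to treatment.

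**Working it through.** No sample size, power or error rate is involved. The check is a comparison of texts and a count.

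**1. Is the table gone?** Protocol 13.2.3.5 calls for statistics on values and on changes. SAP 7.5 gives statistics at baseline only, leaves other values to listings and does not mention changes. The first and third sentences of 7.5 agree with each other only if the third refers to post-baseline values. On that reading, no post-baseline value or change is summarised descriptively.

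**2. Is the change declared?** SAP 7.1 deals only with the timing of looks. It is not declared there.

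**3. Does the rest of the SAP explain it?**
- Small numbers are not the SAP's reason. For the same patients it keeps by-visit values and changes for laboratory tests (7.4), immune status (6.3.3) and growth percentiles (6.3.4).
- The protocol treats neighbouring domains differently. Physical examination findings are to be described as text, and vital signs are to be tabulated. SAP 7.6 lists physical examinations, which fits the protocol. SAP 7.5 does not fit.
- SAP 10.6 already defines change for safety endpoints: from screening for the Adagen group and from the end of the Adagen Lead-in for the EZN-2279 group. SAP 7.5 never uses this for vital signs.

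**4. What does the adverse event route catch?** Protocol 10.4.2 applies two conditions: the change is clinically meaningful, and it meets the adverse event definition. SAP 7.5 speaks of abnormal values and gives no limits. The two filters differ and neither is quantified. Both leave out readings that move but are not judged abnormal or meaningful.

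**5. How many values?**
- Measures (protocol 10.4.2): systolic pressure, diastolic pressure, pulse, respirations, temperature = 5.
- Post-switch treatment visits with vital signs (protocol 11.3 and the SAP study activities table): T-5, T-9, T-13, T-17, T-21 = 5. Week T-1 is taken before the first EZN-2279 dose and belongs to Adagen (SAP 10.2).
- Patients: 6 evaluable.
- Treatment period: 5 × 5 × 6 = 150 values.
- Maintenance, if all six completed the 13 cycles in the example in protocol 11.4: 5 × 13 × 6 = 390 more.

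These counts show how much data the omitted table would have covered. They do not measure bias or a missed signal.

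**6. Which baseline?** SAP 10.4 defines baseline as the last value before the first EZN-2279 dose and restricts the term to efficacy endpoints. Protocol 13.2.3 uses, by default, the last value before the first dose of either study drug. The one summary that SAP 7.5 keeps is therefore at a time point that is unclear for a safety variable.

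**The case against.** A reader might infer that no vital-sign change on this new product would ever be summarised. The documents do not support that. The second sentence of SAP 7.5 sends abnormal values to the adverse event tables, which SAP 7.3 presents by severity and by drug group. All values are listed, SAP Appendix C refers to patient profiles, and the DSMC reviews safety at several points. With about six patients, a within-patient shift can be found by reading the listing.

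Other points also carry weight:
- Vital signs have a modest place in the plan. They are absent from the safety endpoints in protocol 6.3.2 and from the synopsis safety variables.
- Scheduled readings are taken before the weekly dose, about seven days after the previous one, so the table would not show acute effects.
- Patients may range from under 10 years upward, so pooled means of pulse or blood pressure would be hard to read.
- The mock displays are a separate document not available here, so a vital-sign table there cannot be ruled out.
- The protocol does not ask for every visit, an endpoint value or a particular pre-switch reference. Declaring and justifying the omission in SAP 7.1 would also end the discrepancy.

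These points limit the consequence and keep the priority low. They do not remove the contradiction. A table in the mock displays would conflict with SAP 7.5, which would still need correcting. A declaration in 7.1 would make the departure open but would leave measured values without a summary.

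**Conclusion.** The point holds in a limited form. SAP 7.5 departs from protocol 13.2.3.5, and SAP 7.1 does not declare it. The SAP text specifies no by-visit or change-from-baseline summary of vital signs, so shifts below the adverse event threshold are visible only in listings.

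The extent is about 150 scheduled treatment-period values. That assumes exactly six patients, all five post-switch visits completed, and no repeat of Weeks T-5 to T-8 after a dose adjustment. More patients may be enrolled, so the count could be higher. The conclusion rests on the SAP text alone, without the mock displays. It does not mean that vital-sign safety goes unmonitored or that abnormal values go unsummarised. It is a worthwhile correction of low priority and does not threaten the trial's conclusions.

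**What to change.** In SAP 7.5, replace the last sentence with a commitment to descriptive statistics of each vital sign, and of its change, at each scheduled visit and at endpoint. Keep the listing as well.

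- Use the reference points in SAP 10.6: screening for the Adagen group and the end of the Adagen Lead-in for the EZN-2279 group.
- Use the layout of SAP 7.4. The by-visit and endpoint format is a choice made for consistency with the laboratory tables, since the protocol does not prescribe one.
- State which time point baseline means in 7.5, because SAP 10.4 reserves the term for efficacy endpoints.

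If the sponsor prefers to keep listings only, the minimum is to declare and justify that in SAP 7.1.

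The cost is one additional table from data already collected, with no new procedure. The drawback is that pooled means in about six patients of mixed age will have limited interpretability, so the change columns should be read together with the individual listings.
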